3.1.4 Safety endpoints

Following injections are considered as double-blind IMP injections:

• For patients randomized in the placebo group: any injection from double-blind kits;

• For patients randomized in the alirocumab group: any injection from double-blind kits excepted placebo injections given to maintain the blind in case of 2 consecutive LDL-C values <15 mg/dL.

Of note potential additional training injections after randomization using training injection kits will not be taken into account.

The period of safety observation starts from the time when the patient gives informed consent and is divided into three periods:

- PRE-TREATMENT period: defined from the signed informed consent up to the first dose of double-blind IMP injection;
- Treatment-emergent adverse event (TEAE) period: defined as the time from the first dose of double-blind IMP injection to the last dose of double-blind IMP injection +70 days (10 weeks), (as residual effect of treatment is expected until 10 weeks after the stop of double-blind IMP).

The TEAE period will include:

- The TREATMENT period defined as the time from the first dose of double-blind IMP up to the day of last dose of double-blind IMP injection +21 days, as serum concentration of alirocumab >10 μ g/mL is expected for approximately 21 days following administration of 150 mg, and because throughout the previous studies it was observed that when alirocumab concentrations declined below this concentration, decrease in effect on LDL-C is observed.
- The RESIDUAL TREATMENT defined as the time from the day of last dose of double-blind IMP injection +22 days up to the day of last dose of double-blind IMP injection +70 days (10 weeks).
- POST-TREATMENT period: defined as the time starting the day after the end of the TEAE period.

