3.1.5.4 Patients with LDL-C <25 mg/dL (0.65 mmol/L)

The assessment will include:

- The proportion of patients with two consecutive results, spaced out by at least 21 days, of LDL-C <25 mg/dL (<0.65 mmol/L) (respectively LDL-C <15 mg/dL, ie, <0.39 mmol/L) during the double-blind treatment period
- The time to the first LDL-C <25 mg/dL (respectively LDL-C <15 mg/dL) for these patients.

In case both calculated and measured LDL-C are provided for the same sampling, the measured LDL-C will be considered.

3.1.5.5 Anti-alirocumab antibodies assessed throughout the study.

Anti-alirocumab antibodies (ADAs) are assessed at Visit 3 (Month 0), Visit 5 (Month 2), Visit 6 (Month 4), and Visit 10 (Month 12) for the first year, then every year and at the final on-treatment visit (CSED visit for completers, or early end of treatment visit for patients who discontinued the treatment).

ADA measurements will be assigned to analysis windows as defined in Section 3.5.4.

The following variables will be described:

- ADA response (Positive or Negative). For ADA positive:
 - Titer levels
 - Neutralizing status (Positive or Negative)
- Pre-existing positive ADA defined as patients with positive ADA response at baseline with less than 4-fold increase in titer in the post-baseline period
- Treatment-emergent positive ADA response defined as 1) Patients with no ADA positive response at baseline but with any positive response in the post-baseline period (up to follow-up visit) or 2) Patients with a positive ADA response at baseline and at least a 4-fold increase in titer in the post-baseline period (up to follow-up visit). For treatment-emergent positive ADA, the following categories for ADA duration will be applied:
 - A persistent positive response is a treatment-emergent ADA positive response detected in at least 2 consecutive post-baseline samples separated by at least a 16-week period
 - An indeterminate duration positive response is defined as ADA present only at the last sampling time point
 - A transient positive response is defined as any treatment-emergent positive ADA response that is neither considered persistent nor indeterminate

In addition, potential ADA samples that are to be collected after CSED visit for patients with titer \geq 240 at CSED visit will be listed.

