Subgroup of patients with 2 consecutive LDL-C <25 mg/dL (<0.65 mmol/L)

A 2-step approach will be used to analyze the safety in relation to low LDL-C.

The first step will screen events for potential signal using 2 approaches. The first approach will be a direct comparison of patients with 2 consecutive LDL-C <25 mg/dL versus \geq 25 mg/dL (ie, patients without 2 consecutive LDL-C <25 mg/dL) within the alirocumab treatment group. Since these 2 groups are based on post-randomization data with a potential for bias, a second approach will compare the alirocumab effect versus placebo according to categories based on baseline LDL-C. The frequency of patients with 2 consecutive LDL-C <25 mg/dL is expected to be the largest in the category with the lowest baseline LDL-C and be lower and lower in the categories with higher baseline LDL-C. Therefore, an event induced by low LDL-C should be associated with a higher alirocumab effect versus placebo (ie, higher HR) in the first baseline LDL-C category(ies) than in the subsequent categories. Details of these 2 approaches are provided below.

The second step will consist in the comparison of patients with 2 consecutive LDL-C <25 mg/dL versus \geq 25 mg/dL within the alirocumab group for the events detected in the first step, as well as for pre-specified events.

Similar analyses will be provided considering 15 mg/dL (0.39 mmol/L) as threshold instead of 25 mg/dL.

First step

First screening approach

TEAE summary by primary SOC, HLGT, HLT, and PT as well as groupings of events (ie, cataract, neurological events, neurocognitive disorders and "new onset of diabetes" [see Section 3.4.5.3 for the definition]) will be provided on the safety population in the groups below:

- Placebo group
- Alirocumab group
- Alirocumab LDL-C \geq 25 mg/dL (ie, alirocumab patients without 2 consecutive LDL-C <25 mg/dL)
- Alirocumab patients with 2 consecutive LDL-C <25 mg/dL

For patients with 2 consecutive LDL-C <25 mg/dL, analyses will be done on the period starting from the first of the 2 consecutive LDL-C lower than 25 mg/dL to the upper limit of the TEAE period excepted for patients down-titrated from 150 mg to 75 mg for whom the analysis period will end at the date of last injection of 150 mg +70 days (as patients down-titrated from 150 mg to 75 mg are likely to come back above 25 mg/dL).

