The time to the first TEAE/event will be compared for patients with 2 consecutive LDL-C <25 mg/dL versus $\geq 25 \text{ mg/dL}$, within the alirocumab group, using a Cox model, including the covariate for 2 consecutive LDL C <25 mg/dL (Yes/No). Hazard ratio (and 95% CI) from this model will be provided. The event rate per 100 patient-years (the number of patients with an event in question divided by total 100 patient-years) will also be provided.

Second screening approach

TEAE summary by primary SOC, HLGT, HLT, and PT as well as groupings of events (ie, cataract, neurological events, neurocognitive disorders and "new onset of diabetes" will be provided on the safety population according to baseline LDL-C categories (eg, <70, ≥70 to <90, ≥90 to <110, ≥110 mg/dL).

Hazard ratio (and 95% CI) for alirocumab effect versus placebo within each baseline LDL-C subgroup will be provided using a Cox model with baseline LDL-C (in categories), treatment group and the treatment-by-baseline LDL-C interaction term.

To assess the impact of baseline LDL-C on hazard ratio, a Cox model including the baseline LDL-C (as continuous factor), treatment group and treatment-by-baseline LDL-C interaction term will be used. The p-value from the interaction term will be provided for descriptive purpose to evaluate if there is a potential relationship between baseline LDL-C and hazard ratio.

Second step

For each pre-specified event (cataract, neurological events, neurocognitive disorders, new onset of diabetes) as well as for each event with a potential signal detected in the first step, the time to the first TEAE/event will be compared for patients with 2 consecutive LDL-C <25 mg/dL versus \geq 25 mg/dL, within the alirocumab group, using a Cox model, including the covariate for 2 consecutive LDL-C <25 mg/dL (Yes/No) and prognostic factors of the event analyzed. Adjusted HR (and 95% CI) from this model will be provided.

The list of prognostic factors will be established based on the literature and on study data (as applicable).

Subgroups of patients with treatment-emergent ADA positive response

All TEAEs by primary SOC, HLGT, HLT, and PT as well as local injection site reactions will be described in the alirocumab group according to the following ADA parameters:

- Treatment-emergent ADA positive response (yes/no)
- Persistent/transient/indeterminate treatment-emergent ADA positive response.

Analysis of all treatment-emergent serious adverse event(s)

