3.4.7.5 Analyses of anti-alirocumab antibody variables

The following summaries will be performed on the ADA population, taking into account all samples regardless of timing in relation to injections. ADA results will be summarized by treatment group and up-titration status (see Section 3.4.5).

- ADA results (negative or positive) by time point;
- Neutralizing status (negative or positive) by time point for positive ADA;
- ADA titers using descriptive statistics (median, minimum, and maximum) for positive ADA by time point;
- Number (%) of patients with pre-existing ADA and number (%) of patients with treatment-emergent ADA positive response;
- Number (%) of patients with persistent/transient/indeterminate treatment-emergent ADA positive response;
- Time to onset of treatment-emergent ADA positive response using descriptive statistics;

- 11-Oct-2017 Version number: 3
- Number (%) of patients with at least 1 neutralizing ADA.

Correlations between ADA parameters (eg, titers, treatment-emergent ADA positive status, neutralizing status), safety and/or efficacy endpoints will be also explored (eg, scatter plot).

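### Adverse events are tabulated by whether a patient was ever ADA-positive, with no rule that orders events against antibody onset

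*SAP*

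**What the plan says.** The subgroup paragraph on ADA in SAP 3.4.5.1 reads "All TEAEs by primary SOC, HLGT, HLT, and PT as well as local injection site reactions will be described in the alirocumab group according to" two classifications. One is "Treatment-emergent ADA positive response (yes/no"); the other is persistent, transient or indeterminate response.

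SAP 3.1.5.5 defines the first class for most patients as "Patients with no ADA positive response at baseline but with any positive response in the post-baseline period (up to follow-up visit"). Patients already positive at baseline count if their titre rises at least fourfold. No date enters the class. The scheduled sampling times are "Visit 3 (Month 0), Visit 5 (Month 2), Visit 6 (Month 4), and Visit 10 (Month 12) for the first year, then every year"; a further sample is drawn when the patient makes the last visit on treatment. A persistent response is one "detected in at least 2 consecutive post-baseline samples separated by at least a 16-week period".

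The paragraph sets no event window of its own, so the general TEAE period of SAP 3.1.4 applies: "defined as the time from the first dose of double-blind IMP injection to the last dose of double-blind IMP injection +70 days". The default adverse event table in SAP 3.4.5.1 gives the number and percentage of patients. Rates per 100 patient-years are named for other tables, not for these.

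In the same section, the subgroup with two consecutive LDL-C values below 25 mg/dL is handled differently: "analyses will be done on the period starting from the first of the 2 consecutive LDL-C lower than 25 mg/dL". Protocol 11.4.3.1 likewise leaves out events known to precede the first low value.

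**The concern.** Becoming ADA-positive happens after randomization and at a point in time. The tables treat it as a fixed label. An injection-site reaction in Month 1 of a patient first positive at Month 36 is listed as an event in an ADA-positive patient.

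The SAP recognises this problem for low LDL-C. It says that groups formed on post-randomization data may be biased, starts the exposed period at the first low value, and adds rates and a Cox hazard ratio. ADA status is the same kind of variable but gets none of these. SAP 3.4.7.5 describes time to ADA onset, but nothing sets that date against event dates.

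Protocol 10.6.2.1 adds a second link. It calls for an unscheduled ADA sample after cutaneous allergic events and after injection-site reactions that progress or worsen. Patients with exactly the events of interest therefore get an extra chance to test positive, with the event dated before the sample.

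At stake is the reading of the ADA safety tables. Evaluating ADA development is a stated secondary objective, and a reader will use these tables to judge whether antibodies go with reactions.

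**Working it through.** The plan states no figure on this point, so there is none to reproduce.

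**What follows from the text alone.** The first scheduled post-baseline sample is at Month 2. Any event before it must precede the first positive sample, unless an unscheduled or early final sample is taken. For the persistent class, SAP Table 8 targets Months 2 and 4 at days 60 and 122, which are 122 − 60 = 62 days apart. Sixteen weeks is 112 days, so on scheduled visits alone persistence cannot be established before Month 12. That class depends on later samples.

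**Simulation under no antibody effect** (400,000 alirocumab patients per scenario).

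- From the documents: the enrolment table, the 64-month duration, the ADA sampling times, and last dose + 70 days.
- Assumed: 6% ADA-positive by 36 months (early-weighted or constant onset); discontinuation 5–15% per year; first-event hazard 0.02 or 0.3 per year, or an early-weighted injection-site pattern; 0%, 30% or 100% of events stopping treatment.
- Not modelled: samples after treatment stop and event-triggered samples.

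Measures:

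- Crude ratio = (patients with event / patients) among ever-positive ÷ the same among never-positive. Examples: 0.064 / 0.053 = 1.21 (steady events, none stopping treatment) and 0.036 / 0.055 = 0.65 (steady events, all stopping treatment).
- Share before = events in ever-positive patients dated before the first positive sample ÷ all their events.
- Split rate ratio = event rate after the first positive sample ÷ event rate in all other person-time.

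| Event pattern | Crude ratio | Share before | Split rate ratio |
|---|---|---|---|
| Steady, none stop treatment | 1.04–1.21 | 35–67% | 0.98–1.02 |
| Steady, 30% stop | 0.95–1.06 | 30–53% | 0.96–1.00 |
| Steady, all stop | 0.61–0.81 | 12–23% | 0.95–1.02 |
| Early injection-site, none stop | 0.95–1.09 | 58–78% | 0.45–0.61 |
| Early injection-site, 30% stop | 0.86–0.91 | 55–72% | 0.50–0.61 |

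The true ratio is 1 throughout. Median treatment duration is 35–42 months in ever-positive and 31–37 months in never-positive patients. This is why steadily accruing events push the crude ratio up. When events stop treatment, fewer on-treatment samples follow and the patient tends to stay negative, which pushes it down.

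A separate run (5 events per 100 patient-years, 5% per year stopping) shows how much the assumed onset pattern matters. Constant onset at 3% per year gives a ratio of 1.12, with 59% of events before the first positive sample. Early onset (6% of patients, mean 6 months) gives 1.03 and 24%. Measured against true onset, the shares are 48% and 15%, because the first positive sample lags the antibody.

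**Whole-period rates by ever-positive status** are not a remedy. They give 0.97–1.02 for steady events that do not stop treatment, but 0.52–0.94 otherwise.

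**The case against.** The case for leaving the plan alone has several parts.

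- *The tables are descriptive.* They carry no test or hazard ratio, and SAP 3.1.5 labels the ADA endpoints exploratory. This stands and limits the importance of the point. A reader might infer that the SAP attributes these events to antibodies; it does not. It only lists them under ADA-positive.
- *The bias has no fixed direction.* A reader might infer that longer-treated patients look worse by construction. The table above does not support that: the ratio is near 1 for early injection-site reactions and below 1 when events stop treatment.
- *Early leavers can still be found positive.* Protocol 8.3.3, 9.3.1.1 and 10.3.4 continue ADA sampling after permanent discontinuation, and SAP 3.4.7.5 takes all samples regardless of timing relative to injections. So it is wrong to say that only patients who stay on treatment can become positive or persistent. The same provision, however, lets a sample drawn after the TEAE period closes place every earlier event under ADA-positive.
- *A late sample is not a late antibody.* Gaps reach 8 to 12 months, so some events before the first positive sample follow true onset. This stands and is the reason for a sensitivity analysis.
- *Dates are available.* ADA onset time and time to first injection-site reaction are both summarised, and some reactions trigger a sample near the event. But these are separate summaries. The plan also says "Correlations between ADA parameters (eg, titers, treatment-emergent ADA positive status, neutralizing status), safety and/or efficacy endpoints will be also explored", again without ordering one against the other.

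**Conclusion.** The point holds in a limited form. The ADA safety tables count events under an ever-positive label with no onset rule, unlike the low LDL-C tables in the same section. With no antibody effect, about 24–78% of events in ADA-positive patients would precede the first positive sample (12–23% if every event stops treatment), and the crude ratio could lie anywhere from about 0.6 to 1.2. Such a table can suggest an association that is absent or mask one that is present.

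These ranges rest on assumed ADA, event and discontinuation rates and are illustrations, not bounds. That events can be placed in the wrong column follows from the text and needs no assumption. Primary efficacy is untouched. This is a minor, cheap improvement.

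**What to change.** Keep the descriptive table and mark in it which events precede the first positive sample.

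For injection-site reactions, general allergic events and the other Tier 1 groupings, add a Cox model within the alirocumab arm as the main ADA safety comparison. Use time since first dose as the time scale and ADA status as a time-dependent covariate: negative until the first positive sample, positive after. For patients positive at baseline, the switch is the first sample with at least a fourfold titre rise. This compares patients at the same time since first dose, which is what early events need. Do not rely on simple rates per 100 patient-years split at first positivity; for early events they gave 0.45–0.61 with no true effect.

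Add a sensitivity analysis that dates onset from the last negative sample. It also moves a reaction that triggered its own positive sample to the other side of onset. Leave the persistent, transient and indeterminate classes descriptive, since they depend on later samples. State whether samples after the TEAE period count, and whether the denominator is the ADA population of SAP 3.3.3 or the safety population.

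Cost: SAP wording and programming; no new data. Downside: sampling is yearly after Month 12, so onset is dated coarsely.
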